11.2. Standard data derivation

11.2.1. Case definitions

11.2.1.1. Any cause RTI

The subject will be defined as RTI positive when he is presenting one or more of the following items:

- Cough reported in interview during the examination visit or Dica (fields [EXAM VS.SYMP CAT]="Cough" and [EXAM VS.SYMP REP]="Y")
- Runny nose reported in interview during the examination visit or Dica (fields [EXAM_VS.SYMP_CAT]="Runny nose" and [EXAM_VS.SYMP_REP]="Y")
- Blocked nose reported in interview during the examination visit or Dica (fields [EXAM_VS.SYMP_CAT]="Blocked nose" and [EXAM_VS.SYMP_REP]="Y")

11.2.1.1.1. Start of date of RTI case

The start date of the case is defined as the first day of symptoms (i.e. cough, or Runny nose or Blocked nose) based on definitions described in section 11.2.1.1. In case of missing data, for one or 2 of the symptoms, the missing data will be imputed using the earliest date between the non-missing start date for RTI symptoms for this event.

11.2.1.1.2. End date of RTI case

End date of the case is defined as the point at which the subject is considered symptomfree of symptoms.

In case of missing data, for one or 2 of the symptoms, the missing data will be imputed using the latest date between the non-missing end date for RTI symptoms for this event.

11.2.1.2. RSV RTI

RSV RTI status will be defined positive when the subject is RTI positive (see section 11.2.1.1) **AND** RSV positive (see section 6.1.2).

11.2.1.3. All cause RTI with suspicion of involvement of lower respiratory tract

The status RTI with suspicion of involvement of LRTI will be assessed using data from surveillance visit and data from examination visit.

200150 (EPI-RSV-005 BOD)

Statistical Analysis Plan Amendment 1 Final

The subject will be considered positive for RTI with suspicion of involvement of LRTI:

- positive for RTI at surveillance visit AND positive for a suspicion of involvement of LRTI at surveillance visit
- AND/OR when the subject has attended an examination visit (whatever LRTI final assessment)

The subject will be defined as positive for RTI at surveillance visit when he is presenting one or more of the following items:

- Did or does the child cough? (fields [SRV_RTI.CATEGORY] ="Cough" and [SRV_RTI.QUEST_YN]=Y")
- And/or did or doe s the child have runny nose? (fields [SRV_RTI.CATEGORY] ="Runny nose" and [SRV_RTI.QUEST_YN]=Y")
- And/or did or doe s the child have a blocked nose? (fields [SRV_RTI.CATEGORY] ="Blocked nose" and [SRV_RTI.QUEST_YN]=Y")

The subject will be considered positive for a suspicion of involvement of LRTI when he subject has attended an examination visit (whatever LRTI final assessment) or when he has one or several of the following items is reported in interview during the surveillance visit:

- Did or does the child make noises like wheezing or grunting when breathing? (fields [SRV_RTI.CATEGORY] ="Wheezing or grunting" and [SRV_RTI.QUEST_YN]=Y")
- And/or did or does the child breathe faster than normal? (fields [SRV_RTI.CATEGORY] ="Breathe faster" and [SRV_RTI.QUEST_YN]=Y")
- And/or did or does the child flare his/ her nostrils when breathing? (fields [SRV_RTI.CATEGORY] ="Flare Nostrils" and [SRV_RTI.QUEST_YN]=Y")
- And/or did or does the child use his/ her muscles in chest and neck when breathing? (fields [SRV_RTI.CATEGORY] ="Use muscles" and [SRV_RTI.QUEST_YN]=Y")
- And/or was or is the child short of breath? (fields [SRV_RTI.CATEGORY] ="Short of breath" and [SRV_RTI.QUEST_YN]=Y")

11.2.1.4. LRTI

11.2.1.4.1. Any LRTI (WHO definition)

The subject will be defined as LRTI positive according to WHO definition when he is presenting:

- history of cough or difficulty breathing,
- and a measured oxygen saturation < 95% or an increase of respiratory rate.

200150 (EPI-RSV-005 BOD)

Statistical Analysis Plan Amendment 1 Final

For derivation purposes we are characterizing 2 groups of items:

- Component A which gathers items used to derive history of cough and difficulty breathing,
- Component B which gathers the oxygen saturation and respiratory rate.

Component A:

The subject will be considered positive for Component A when one or several of the following items are reported in interview during the examination visit:

- Cough reported in interview during the examination visit or Dica (fields [EXAM_VS.SYMP_CAT]="Cough" and [EXAM_VS.SYMP_REP]="Y")
- And/or difficulty breathing as defined in section 11.2.2.1

Please note that the 2 symptoms: blocked nose and runny nose are not considered here for the derivation, indeed even if in the table 1 note 1 the case definition mentioned "Based on history reported by parents/LARs and includes difficulty breathing associated with nasal obstruction". (in fact it relates to how the data is intended to be collected in future trials where the mother is asked does the child have difficulty breathing yes or no. It is meant to qualify that if the child's breathing difficulty is due to only blocked nose if the mother says its difficulty breathing it is. However, in this study we don't have the question difficulty breathing and so we cannot know whether the blocked nose was or not associated with difficulty breathing in the mothers view)

Component B:

The subject will be considered positive for Component B when one or both of the following statement is reached:

- Blood Oxygen Saturation <95% (field [CLN_SGN2.BLSAT_V])
- And/or Increased Respiratory rate as defined in section 11.2.2.2

Please note that Blood Oxygen Saturation and respiratory rate are measured during the examination visit.

The subject will be defined as LRTI positive according to WHO definition when he is positive for Component A AND positive for Component B.

11.2.1.4.2. Severe LRTI (WHO definition)

Severe LRTI status will be defined positive when the subject is LRTI positive (see section 11.2.1.4.1) AND present one or both of the 2 following items:

• Blood Oxygen Saturation <93% (field [CLN_SGN2.BLSAT_V])

Statistical Analysis Plan Amendment 1 Final

• **AND/OR** Any chest indrawing present at examination visit (fields [CLN_SIGN.SIGN_CAT]="Chest indrawing" and [CLN_SIGN.SIGN_YN]="Y")

Please note that the chest indrawing symptom used to define severity is the one measured by the medical team during the examination visit.

11.2.1.4.3. Any LRTI (GSK case definition)

The subject will be defined as LRTI positive according to GSK case definition when he is presenting:

• RTI as defined in section 11.2.1.1

AND at least one or both of the following:

- Blood Oxygen Saturation <95% (field [CLN_SGN2.BLSAT_V])
- And/or Increased Respiratory rate as defined in section 11.2.2.2

11.2.1.4.4. Severe LRTI (GSK case definition)

Severe LRTI status according to GSK case definition will be defined positive when the subject is LRTI positive according to GSK case definition (see section 11.2.1.4.3) AND present at one of the following items:

- Blood Oxygen Saturation <92% (field [CLN_SGN2.BLSAT_V])
- **AND/OR** Irritability/agitation present at examination visit (fields [CLN_SIGN.SIGN_CAT]="Irritability" and [CLN_SIGN.SIGN_YN]="Y")
- **AND/OR** Lethargy/sleepiness present at examination visit (fields [CLN_SIGN.SIGN_CAT]="Lethargy" and [CLN_SIGN.SIGN_YN]="Y")
- **AND/OR** Any chest indrawing present at examination visit (fields [CLN_SIGN.SIGN_CAT]="Chest indrawing" and [CLN_SIGN.SIGN_YN]="Y")
- **AND/OR** Reduced/no vocalisation present at examination visit (fields [CLN SIGN.SIGN CAT]="No vocalisation" and [CLN SIGN.SIGN YN]="Y")
- **AND/OR** Apnoea > 20 sec present at examination visit (fields [CLN_SIGN.SIGN_CAT]="Apnoea" and [CLN_SIGN.SIGN_YN]="Y" and [CLN_SIGN.APNOEA20]="Y")
- **AND/OR** Cyanosis present at examination visit (fields [CLN_SIGN.SIGN_CAT]="Cyanosis" and [CLN_SIGN.SIGN_YN]="Y")
- **AND/OR** Stop feeding well present at examination visit (fields [CLN_SIGN.SIGN_CAT]="Stop feeding" and [CLN_SIGN.SIGN_YN]="Y").

Please note that the symptom used to define severity is the one measured by the medical team during the examination visit.

11.2.1.4.5. Any LRTI (Nokes definition)

The subject will be defined as LRTI positive according to Nokes definition when he is presenting:

- history of cough or difficulty breathing,
- and at least one of the following:
 - Fast breathing, or
 - Indrawing, or
 - Low oxygen saturation (< 90%) by pulse oxymetry when accompanied by a clinical diagnosis of LRTI or bronchiolitis.

For derivation purposes we are characterizing 2 groups of items:

- Component A which gathers items used to derive history of cough and difficulty breathing,
- Component B which gathers Fast breathing, Indrawing, Low oxygen saturation (< 90%) by pulse oxymetry when accompanied by a clinical diagnostic of LRTI or bronchiolitis.

Component A:

The subject will be considered positive for Component A when one or several of the following items is reported in interview during the examination visit:

- Cough reported in interview during the examination visit or Dica (fields [EXAM_VS.SYMP_CAT]="Cough" and [EXAM_VS.SYMP_REP]="Y")
- And/or difficulty breathing as defined in section 11.2.2.1

Component B:

The subject will be considered positive for Component B when at least one of the following statements is reached:

- Increased Respiratory rate as defined in section 11.2.2.2
- **AND/OR** Any chest indrawing present at examination visit (fields [CLN_SIGN.SIGN_CAT]="Chest indrawing" and [CLN_SIGN.SIGN_YN]="Y").
- **AND/OR** Low oxygen saturation (< 90%) by pulse oxymetry (field [CLN_SGN2.BLSAT_V]) associated with clinical diagnostic of respiratory infection. (fields [CLN_DIAG.DIAG_YN]="Y")

11.2.1.4.6. Severe LRTI (Nokes definition)

The subject will be considered positive Severe LRTI according to Nokes definition when the subject is LRTI positive according to Nokes case definition (see section 11.2.1.4.5) and when at least 2 of the following statements are reached:

- Any chest indrawing present at examination visit (fields [CLN_SIGN.SIGN_CAT]="Chest indrawing" and [CLN_SIGN.SIGN_YN]="Y").
- AND/OR Low oxygen saturation (< 90%) by pulse oxymetry (field [CLN_SGN2.BLSAT_V]) associated with clinical diagnostic of respiratory infection. (fields [CLN_DIAG.DIAG_YN]="Y")

11.2.1.4.7. Start date of LRTI case

The start date of the case is defined as the first day of symptoms (e.g. cough, or difficulty breathing) based on definitions.

In case of missing data, for one or more of the symptoms, the missing data will be imputed using the earliest date between the non-missing start date of LRTI symptoms for this event.

11.2.1.4.8. End date of LRTI case

End date of the case is defined as the point at which the subject is considered symptomfree of symptoms (e.g. cough, or difficulty breathing).

In case of missing data, for one or more of the symptoms, the missing data will be imputed using the latest date between the non-missing end date of LRTI symptoms for this event.

11.2.1.5. RSV RTI with suspicion of involvement of lower respiratory tract

The RSV status will be assessed at the examination visit, and the status RTI with suspicion of involvement of LRTI will be assessed using data from surveillance visit and data from examination visit.

The subject will be considered positive for RSV RTI with suspicion of involvement of LRTI:

- When he is positive for RSV (see section 6.1.2)
- AND positive for RTI with suspicion of involvement of LRTI (see section 11.2.1.3)

11.2.1.6. RSV-LRTI

RSV-LRTI status will be defined positive when the subject is RSV positive (see section 6.1.2) **AND** LRTI positive according to each of the LRTI case definitions (WHO see section 11.2.1.4.1, GSK see section 11.2.1.4.3, Nokes see section 11.2.1.4.5). In addition an exploratory RSV LRTI was defined see Table 4 Summary of case definitions. 4 RSV-LRTI statuses will be defined:

- RSV-LRTI according to WHO definition
- RSV-LRTI according to GSK definition
- RSV-LRTI according to Nokes definition
- RSV-LRTI according to Exploratory definition

The Figure 2 shows how is derived the start date of event and its duration according to the start date and duration of the corresponding LRTI event.

Figure 2 Derivation of RSV-LRTI events date and duration according to the the corresponding LRTI event

11.2.1.7. RSV severe LRTI

RSV Severe LRTI status will be defined positive when the subject is RSV positive (see section 6.1.2) **AND** Severe LRTI positive according to each of the Severe LRTI case definitions (WHO see section 11.2.1.4.2, GSK see section 11.2.1.4.4, Nokes see section 1). In addition an exploratory case definition for RSV severe LRTI was defined in Table 4. 4 RSV Severe LRTI statuses will be defined:

- RSV Severe LRTI according to WHO definition
- RSV Severe LRTI according to GSK definition
- RSV Severe LRTI according to Nokes definition
- RSV Severe LRTI according to Exploratory defintion

11.2.1.8. RSV hospitalization

RSV hospitalization status will be defined positive when the subject is RSV positive (see section 6.1.2) **AND** if he has been hospitalized after examination visit.

The subject will be considered to be hospitalized if the medical attendance is defined as one of the following:

- Inpatient clinic (Hospitalisation) Intensive care (field [MED_ATD.MEDATD_TXT]="Inpatient clinic (Hospitalisation) - Intensive care")
- Inpatient clinic (Hospitalisation) Medium care (field [MED_ATD.MEDATD_TXT]="Inpatient clinic (Hospitalisation) - Medium care")
- Inpatient clinic (Hospitalisation) Regular care (field [MED_ATD.MEDATD_TXT]="Inpatient clinic (Hospitalisation) - Regular care")
- Inpatient clinic (Hospitalisation) Ventilation (field [MED_ATD.MEDATD_TXT]="Inpatient clinic (Hospitalisation) - Ventilation")
- Inpatient clinic (Hospitalisation) nebulization (field [MED_ATD.MEDATD_TXT]="Inpatient clinic (Hospitalisation) - nebulization")

Please note that if the subject has been admitted to

- *Emergency Room* (field [MED_ATD.MEDATD_TXT]="*Emergency Room*")
- *General Practitioner* (field [MED_ATD.MEDATD_TXT]="*General Practitioner*")
- *Outpatient Clinic* (field [MED_ATD.MEDATD_TXT]="*Outpatient Clinic*")

He will not be considered as hospitalized.

The Figure 3 shows how is derived the start date of RSV-Hospitalization event and its duration.

Figure 3 Derivation of RSV-Hospitalization events date and duration

11.2.1.9. RSV LRTI hospitalization

RSV LRTI hospitalization status will be defined positive when the subject is RSV hospitalization positive (see section 11.2.1.8) AND if he is positive for WHO LRTI (see section 11.2.1.4.1).

The Figure 4 shows how is derived the start date of RSV-LRTI Hospitalization event and its duration according to the corresponding LRTI event.

Figure 4 Derivation of RSV-LRTI hospitalization events date and duration according to the corresponding LRTI event

11.2.1.10. RSV severe LRTI hospitalization

RSV LRTI hospitalization status will be defined positive when the subject is RSV hospitalization positive (see section 11.2.1.8) AND if he is positive for WHO Severe LRTI (see section 11.2.1.4.2).

The Figure 5 shows how is derived the start date of RSV-severe LRTI Hospitalization event and its duration according to the corresponding LRTI event.

Figure 5 Derivation of RSV LRTI hospitalization events date and duration according to the corresponding LRTI event

11.2.1.11. Visit for worsening of symptoms assessment

All symptoms collected from initial visits and during follow up of worsening of symptom visits are combined and counted as one episode with the most severe grade. The earliest date of reported symptom will be used as the start date of the episode. The latest date of reported symptom will be used as the end date of episode.

A worsening visit that is greater than 21 days after the initial visit will be count as a separate episode instead of worsening visit.

11.2.1.12. New episode rule

A new episode of an event is a single case of RTI, LRTI, severe LRTI, or hospitalization meeting the respective case definitions and severity scale with an interval of at least 7 symptom free days since the last episode that was diagnosed.

As mentioned in the section 11.2.1.11, any worsening visit that is greater or equal to 21 days after the initial visit will count as a new episode.

For example, Figure 6 and Figure 7 show how LRTI events are derived depending on the duration of symptoms free period.

Figure 6 Derivation of 2 LRTI events date and duration with a symptom free period of at least 7 days

Figure 7 Derivation of 2 LRTI events date and duration with a symptom free period below 7 days

200150 (EPI-RSV-005 BOD)

Statistical Analysis Plan Amendment 1 Final Please note that in this SAP, recurrent events are not persistent events, they are independent (new) events.

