The start date of the case is defined as the point at which the LRTI was first identified as a potential LRTI by the investigator/study staff during an active or passive surveillance study contact, and if the LRTI is subsequently confirmed by the investigator/study staff (according to the LRTI case definition and severity scale for surveillance) during the examination visit (off-site/site).

End date of the LRTI case:

End date of the case is defined as the point at which the subject is considered symptomfree of difficulty in breathing, based on the data provided by the parent(s)/LAR(s) in the diary card and any additional data obtained from healthcare providers involved in management of the case.

New case of LRTI:

A new, single case of LRTI is any occurrence of an LRTI case meeting the LRTI case definition and severity scale with an interval of at least 7 symptom free days since the last episode of LRTI that was diagnosed.

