6.5.17. Return Diary card at completion or at case resolution

The diary card will be collected at completion.

- Regular completion is after the standard diary card duration of 14 days.
- If a surveillance case eCRF is 'closed' due to a subsequent examination visit for the same case, the diary card relating to the 'closed' eCRF is stopped prematurely and a new 14-day diary card is started (see also Section 3-examination visit).

If the subject is not free of the symptoms asked for in the diary card at the end of Day 14, the parent(s)/LAR(s) should continue to assess the symptoms until no more symptoms are present, and record in the diary card, the date at which no more symptoms were observed in the child.

6.5.18. Confirmation and expansion of data on healthcare utilization occurring after the examination visit (off-site/site) and collection of any further, relevant data on disease course with HCPs involved in subject care

Data on disease course recorded by the subject's parent(s)/LAR(s) in the diary card until diary card completion/case resolution should be assessed and recorded by the investigator/study staff in the subject's eCRF.

Data provided by the parent(s)/LAR(s) in the diary card on healthcare utilization should be confirmed by direct contact of the investigator/study staff with the healthcare providers involved in management of the case (e.g. GP, hospital staff), and recorded in the eCRF. Wherever possible, the data on healthcare utilization should be made more complete so as to best capture the healthcare utilization in the eCRF. Any clinical diagnoses for the respiratory infection (e.g. pneumonia, bronchiolitis) made by the contacted healthcare providers should be collected and recorded in the eCRF as well as the symptoms assessed in support of this diagnosis (especially measured RR and SaO2).

Note: In case of any discrepancies between healthcare utilization data recorded in the diary card and as provided (and supported with source documentation) by the HCPs, the data from the HCP will be used in the eCRF.

Data from healthcare providers (such as temperature, RR, SaO2, symptoms and diagnosis) is to be regarded as a valuable, but optional extra, if this data is available and shared by the applicable healthcare provider.

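### SAP 11.2.1.11 and 11.2.1.12 let a late worsening visit start a new episode without symptom-free time, contrary to the 7-day rule and with no stated precedence

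*SAP*

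**What the plan says.** Protocol 4.1 defines a new LRTI case as one that meets the case definition "with an interval of at least 7 symptom free days since the last episode of LRTI that was diagnosed". It gives no alternative based on elapsed time. The same section ends a case when the child no longer has difficulty in breathing.

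SAP 11.2.1.12 extends the rule to RTI, LRTI, severe LRTI and hospitalization, again "with an interval of at least 7 symptom free days since the last episode that was diagnosed". Its next sentence, presented as a restatement of 11.2.1.11, says that "any worsening visit that is greater or equal to 21 days after the initial visit will count as a new episode". SAP 11.2.1.11 itself first pools the initial and worsening visits of an illness into one episode at the worst grade, then makes an exception: "A worsening visit that is greater than 21 days after the initial visit will be count as a separate episode instead of worsening visit". Neither 21-day sentence mentions symptom-free time. Section 11.2.1.12 closes by saying that "recurrent events are not persistent events, they are independent (new) events".

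SAP 11.2.1.4.8 ends an LRTI case when symptoms have gone, naming cough and difficulty breathing as examples. SAP section 9, which lists departures from the planned analyses, mentions neither the 21-day rule nor the wider set of symptoms used for the end date.

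**The concern.** The episode is the unit of count in every analysis that is not restricted to first events. Two rules for when one episode ends and the next begins, with no order between them, can give different counts from the same data. One of the two can turn a single unresolved illness into two episodes.

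The co-primary analyses at stake are healthcare utilization (SAP 6.7, all episodes including recurrent ones) and agreement between case definitions (SAP 6.8.1, all new events including recurrent ones). The all-episode viral load tables under SAP 6.8.2 use the same unit. In the utilization tables, SAP 11.2.4 keeps only the most intense attendance per event. A split illness whose two parts both qualify therefore contributes two rows to the denominator and may place them in different care categories. In the agreement tables it contributes two entries from one child and one illness.

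**Working it through.** The plan gives no figure that depends on this rule, so there is nothing to reproduce. The check is to apply each rule to the same timelines.

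**Inputs**
- Rule A, protocol 4.1 and the first sentence of SAP 11.2.1.12: new episode if symptom-free days are at least 7.
- Rule B, SAP 11.2.1.11: new episode if days from the initial visit to the worsening visit exceed 21.
- Rule C, second rule in SAP 11.2.1.12: new episode if those days are 21 or more.
- Timelines are illustrative. The initial visit is on day 0 and the later visit is recorded as a worsening visit.

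**Results (number of episodes)**

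| Later visit | Symptom-free days between | Rule A | Rule B | Rule C |
|---|---|---|---|---|
| Day 20 | 0 | 1 | 1 | 1 |
| Day 21 | 0 | 1 | 1 | 2 |
| Day 25 | 0 | 1 | 2 | 2 |
| Day 25 | 10 (free on days 10 to 19) | 2 | 2 | 2 |

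The second row is the conflict between the two SAP sections: 21 is not greater than 21, but it is equal to 21. The third row is the conflict with the protocol: 25 is greater than 21, while 0 symptom-free days is fewer than 7. The last row shows that the rules agree when a 7-day gap is present. The disagreement is confined to worsening visits at day 21 or later with fewer than 7 symptom-free days before them.

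**Internal consistency.** In the third row, the second episode is the same illness persisting. That is what the closing statement of SAP 11.2.1.12 says a recurrent event is not.

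**Are symptom dates available?** Protocol 6.5.17 says that, if symptoms remain at the end of Day 14, parents "should continue to assess the symptoms until no more symptoms are present" and record the date on which they stopped. SAP 11.2.1.4.8 imputes missing symptom end dates from those recorded for the same event. The 7-day test can therefore be derived without an elapsed-time substitute.

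**Which counts can move.** SAP 11.2.1.12 requires a new episode to meet its own case definition. For RSV LRTI this means low saturation or a raised respiratory rate at examination (for example, SAP 11.2.1.4.1) and an RSV-positive swab (SAP 11.2.1.6 and 6.1.2). The split adds an RSV LRTI episode only when the later visit passes both tests. The Kaplan-Meier estimates (SAP 6.6.1) and monthly incidence proportions (SAP 11.1.4) use each child's first episode, so a split-off second episode does not inflate them.

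**The case against.** The strongest reply is that the SAP never says the 21-day rule overrides the 7-day rule. It states both, then refers to Figures 6 and 7, whose captions concern only a symptom-free period of at least or below 7 days. The figures themselves are not shown in the text available here and might settle how the rules combine. This stands as far as it goes: a reader might infer an explicit override, and the documents do not state one. The second rule is nevertheless worded without condition, so a programmer following it literally would split the day-25 illness.

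Four stronger readings are tempting and are not supported.
- *Every such illness adds one episode.* Not for the RSV LRTI tables, because a later visit with a negative swab, or with normal saturation and respiratory rate, adds nothing there.
- *A persistent illness crossing 6 or 12 months is counted as a first episode in both age intervals.* SAP 11.2.1.4.7 and 11.2.1.11 date episodes from symptoms, not from visits, and the SAP does not say what start date a split-off episode carries. The effect is possible but not established.
- *The SAP merges cases that the protocol separates, because a lingering cough delays the SAP end date.* That requires reading the protocol's unqualified phrase about symptom-free days as free of difficulty in breathing. The protocol uses the narrower wording only for the end date.
- *The inflation can be put as a percentage.* The documents give no count of late worsening visits.

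It is also fair that protocol 9.5 leaves derived variables to the SAP and that protocol 9.10 provides for deviations to be described in the final report. The new-case definition, however, is fixed in protocol section 4, and SAP section 9 was the place to declare a change to it.

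**Conclusion.** The point holds in a limited form. SAP 11.2.1.11 and 11.2.1.12 add an elapsed-time rule that the protocol does not contain, give it no precedence relative to the 7-day rule, disagree with each other at day 21, and do not declare it. Followed as written, they can split one unresolved illness into two episodes, which contradicts the SAP's own description of recurrent events.

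The exposure is in the all-episode analyses, principally the co-primary utilization and agreement tables. For RSV LRTI counts it is limited to later visits that meet the case definition with a positive swab. The size is unknown, and no effect on any utilization percentage or agreement measure has been shown. The conclusion rests on taking the 21-day sentences at their literal wording and on there being some worsening visits at day 21 or later without a 7-day gap.

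The differing end-date symptoms in protocol 4.1 and SAP 11.2.1.4.8 are a related ambiguity that needs settling, because they determine when symptom-free days begin to count.

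**What to change.** Write one rule and use it in both SAP 11.2.1.11 and 11.2.1.12: a visit at or after day 21 starts a new episode only if at least 7 symptom-free days intervened; otherwise it is merged with the initial episode.

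State which symptoms define symptom-free for each event type, and reconcile protocol 4.1 with SAP 11.2.1.4.8. A clock based on difficulty in breathing alone would not serve. Under SAP 11.2.1.4.1, WHO LRTI can be met by cough with low saturation or a raised respiratory rate, and 11.2.1.12 also governs RTI and hospitalization.

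If the sponsor prefers to keep the 21-day split, use a single inequality in both sections, declare the rule in SAP section 9 as a departure from protocol 4.1, state the start date given to a split-off episode, and report the all-episode counts under both rules. That comparison would supply the size that is now unknown.

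The cost is SAP wording, one changed derivation and, if the split is kept, one extra set of counts. No new data are needed.
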